### **6.3.1 Procedures for maintaining and breaking the treatment blind**

#### **6.3.1.1 Maintenance of study treatment blind**

All participant treatment details will be allocated and maintained by the IRT system.

#### **6.3.1.2 Breaking the treatment blind in an emergency situation**

In the event of an emergency, it will be possible to determine to which treatment arm and dose the participant has been allocated by contacting the IRT. All sites will be provided with details of how to contact the system for code breaking at the start of the study.

The Clinical Project Manager will be informed immediately via the IRT when a code is broken, but will remain blinded to specific treatment information. Any unblinding of the study medication performed by the Investigator must be recorded in the source documents and on the Study Termination eCRF page.

### **6.4 Treatment compliance**

At each in-clinic visit after study medication is dispensed, participants must return all unused study medication and empty study medication containers. Drug accountability must be done in the participant's presence in order to obtain explanations regarding discrepancies in compliance with the dosing regimen. Drug accountability must be recorded on the Drug Accountability form.

If a participant is found to be persistently noncompliant (<80% or >120% compliant), the Sponsor, in conjunction with the Investigator, will make a decision as to whether the participant should be withdrawn from the study.

### **6.5 Concomitant medication(s)/treatment(s)**

#### **6.5.1 Permitted concomitant treatments (medications and therapies)**

DaTSCAN tracer for DaT-SPECT imaging will be sourced from GE-Healthcare via Invicro. The tracer is approved for commercial use in Europe, the US, and Canada and will be used according to the product label. Approximate radioactivity per dose is 185 MBq.

Thyroid-blocking agents such as Lugol must be applied before DaT-SPECT.

Should a COVID-19 vaccine be administered during study participation, full details will be recorded in the concomitant medication eCRF page. The specific name of the vaccine and the exact date of administration should be recorded, as instructed in the completion guideline.

#### **6.5.2 Prohibited concomitant treatments (medications and therapies)**

No concomitant medications for the treatment of motor symptoms of PD or medications with PD disease modifying effect will be allowed at inclusion (eg, levodopa, COMT inhibitors, dopamine agonists, MAO-B inhibitors). For rescue treatment of PD symptoms, refer to Section 6.5.3.

Strong CYP3A4 inhibitors and inducers, as well as sensitive CYP3A4 substrates with narrow therapeutic index are not allowed during the study.

The following medications are not allowed during the 50 days before DaT-SPECT imaging:

- Metoclopramide
- Alpha methyldopa

- Clozapine
- Olanzapine
- Flunarizine
- Amoxapine
- Amphetamine derivatives
- Reserpine
- Bupropion
- Buspirone
- Cocaine
- Mazindol
- Methylamphetamine
- Methylphenidate
- Norephedrine
- Phentermine
- Phenylpropanolamine
- Modafinil

### **6.5.3        Rescue medication**

Investigators will be encouraged to carefully document all changes and dose adaptations, particularly when considering ST initiation which should always consider the individual participant needs and standard of care recommendations. Guidance on the initiation of rescue medication will be provided in a separate manual.

The study site will supply rescue medication that will be obtained locally.

Levodopa is determined as first choice for participants who are determined to require ST. Other ST options are only permitted in exceptional cases, where levodopa has an unsatisfactory effect, where contraindications against levodopa are identified by the Investigator, or where an alternative ST drug is medically indicated for any other reason. Monoamine Oxidase Type B inhibitors will not be allowed.

The date and time of onset of rescue medication administration, as well as the name and dosage regimen of the rescue medication, must be recorded in the eCRF. Any dose adjustments also need to be recorded.

For all scheduled visits, study participants that start to receive ST over the study observation period will be asked to refrain from taking ST for at least 12 hours before the clinic visit and to bring the medication to the site. A 12-hour washout is considered sufficient to achieve a practically defined off-state for the range of STs specified in this section and has proven tolerable in clinical practice (Bloem et al, 2019). All tests which are expected to be sensitive to the effects of ST will take place throughout the first part of the study visit to allow resuming

dosing of ST at the earliest possible point. If a participant does not comply with the 12-hour ST washout prior to any visit, the data from that particular visit will be censored.

## **6.6 Dose modification**

There is no dose modification allowed in PD0053.

## **6.7 Criteria for study hold or dosing stoppage**

UCB will halt further dosing for all study participants at all sites if any of the following criteria are met during the course of the study and following case review to confirm causality and seriousness and/or severity of reported events.

Possible reasons for discontinuation or suspension of the study include (but are not limited to):

1. A pattern of AEs, abnormal lab results, or other safety findings that would be unacceptable for this patient population.
2. A pattern of hypersensitivity reactions that are considered study medication-related and that would be unacceptable for this patient population.

If any criterion is potentially met, the SMC will request for the DMC to meet as soon as possible to make a recommendation to the Sponsor as to whether discontinuation, pausing, or suspension of IMP dosing or the study should occur.

Consideration will be given to severity and relatedness of events. Further details on the role and process of ensuring close safety monitoring through the DMC are provided in the DMC charter.

3. If the Sponsor or its designees judges it necessary for medical, safety, regulatory, or any other reasons consistent with applicable laws, regulations, and Good Clinical Practices (GCP).
4. Sponsor's decision that continuation of the study is unjustifiable for medical or ethical reasons.
5. Discontinuation of development of the Sponsor's study medication.

Detailed procedures for reporting SAEs and other safety events which may meet study hold criteria are provided in Appendix 3 (Section 10.3).

## **6.8 Treatment after the end of the study**

Study participants who complete the Treatment Period will have the option to transition into a dose-blinded extension study (PD0055). In this case, participants will not enter the SFU Period of PD0053. For those participants who do not roll over to PD0055, the study ends with an SFU Visit (Visit 16) approximately 30 days after the last dose. In case of early termination of a participant's study medication, the participant will be asked to attend the EOT and the SFU Visit (30 days after the last dose) and will not be eligible for PD0055.

## 7

# DISCONTINUATION OF STUDY MEDICATION AND PARTICIPANT DISCONTINUATION/WITHDRAWAL

## 7.1 Discontinuation of study medication

Study medication will be stopped if the study participant develops a medical condition (or laboratory abnormality or ECG change) that, in the opinion of the Investigator, compromises the study participant's ability to participate or compromises the study participant's safety.

Any new clinically relevant safety finding should be reported as an AE.

In all cases, the study participant should be followed until the condition has resolved as agreed by the Investigator and the UCB Study Physician.

See the Schedule of Activities (Section 1.3) for data to be collected at the time of treatment discontinuation and follow up and for any further evaluations that need to be completed.

### 7.1.1 Hypersensitivity reaction (such as rash, angioedema, or anaphylaxis)

Study participants will be informed that if they develop any symptoms suggestive of a hypersensitivity reaction (eg, rash, angioedema, or anaphylaxis) they should contact the Investigator immediately.

The Investigator should assess the presenting symptoms to determine if this is possibly a hypersensitivity reaction.

[figure not shown]
If the event is not considered to be a hypersensitivity reaction (eg, a rash due to another cause) the Investigator should document this and the participant may continue dosing.

If the event is possibly a hypersensitivity reaction the Investigator should advise the participant to withhold dosing and arrange additional investigations as per Section 8.3.6.1. The event should be reported to UCB as an AESI. In this scenario dosing may only be recommenced following agreement of the Investigator and the SMC.

### 7.1.2 Liver Chemistry Stopping Criteria

Discontinuation of study medication for abnormal liver function should be considered by the Investigator when a participant meets one of the conditions outlined in Figure 7-1 or if the Investigator believes that it is in best interest of the participant.

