**Figure 7-1: Phase 2 liver chemistry stopping criteria and increased monitoring algorithm**

ALT=alanine aminotransferase; AST=aspartate aminotransferase; INR=international normalized ratio; SAE=serious adverse event; ULN=upper limit of normal.

Specific assessments and follow up actions for potential drug-induced liver injury are provided in Appendix 6 (Section 10.6).

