### **7.2           Participant Discontinuation/Withdrawal from the study**

Participants are free to withdraw from the study at any time, without prejudice to their continued care.

A participant may withdraw from the study at any time at his/her own request, or may be withdrawn at any time at the discretion of the Investigator, SMC, or DMC for safety, behavioral, compliance, or administrative reasons.

If the participant withdraws consent for disclosure of future information, the Sponsor may retain and continue to use any data collected before such a withdrawal of consent.

If a participant withdraws from the study, he/she may request destruction of any samples taken and not tested, and the Investigator must document this in the site study records.

See the Schedule of Activities (Section 1.3) for data to be collected at the time of study discontinuation and follow-up, and for any further evaluations that need to be completed. The DaT-SPECT will occur at EOT (End of Treatment), provided that the previous DaT-SPECT occurred more than 6 months prior to EOT visit.

Participants should be withdrawn from the study if any of the following events occur:

1. Withdrawal of consent by the study participant
2. A regulatory agency requests withdrawal of the participant from the study
3. Loss of ability to freely provide consent through imprisonment or involuntarily incarceration for treatment of either a psychiatric or physical (eg, infectious disease) illness or throughout quarantine conditions.

Participants must be discontinued from study medication (but not necessarily from the study) if any of the following occurs:

1. Study participant develops an illness that would interfere with his/her continued dosing.

2. Study participant takes prohibited concomitant medications as defined in the protocol. Outcome should be decided on a case-by-case basis.
3. There is confirmation of a pregnancy during the study, as evidenced by a positive pregnancy test.
4. Study participant has actual suicidal ideation since last visit as indicated by a positive response (“Yes”) to either Question 4 or Question 5 of the “Since Last Visit” version of C-SSRS. The study participant should be referred immediately to a mental healthcare professional and must be discontinued from study medication.

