5. Study participant is confirmed positive for recreational drug use or for alcohol at a Baseline Visit (Day 0), which is deemed significant enough to impair the study participant’s safety or the quality of the collected data. Outcome should be decided on a case-by-case basis.
6. Renal toxicity considered possibly related to the IMP. Laboratory tests suggestive of renal toxicity which should trigger further assessment may include:
  - Increase in serum creatinine  $\geq 0.3\text{mg/dL}$  OR
  - Increase in serum creatinine to  $\geq 1.5$  times from Baseline OR
  - New persistent albuminuria or clinically significant increase in pre-existing albuminuria, over 6 consecutive weeks

Any clinically significant findings in laboratory results for renal function will be monitored until resolution or stabilization.

7. The Sponsor requests withdrawal of the participant.
8. Study participant takes part in any other interventional study during the duration of this study.

Investigators should contact the Medical Monitor, whenever possible, to discuss the withdrawal of a participant in advance.

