## 10.6 Appendix 6: Liver safety – suggested actions and follow-up assessments

Participants with potential drug-induced liver injury must be assessed to determine if study medication must be discontinued. In addition, all concomitant medications and herbal supplements that are not medically necessary should also be discontinued.

Investigators should attempt to obtain information on study participants in the case of study medication discontinuation to complete the final evaluation.

Study participants with potential drug-induced liver injury should not be withdrawn from the study until investigation and monitoring are complete. All results of these evaluations and observations, as well as the reason(s) for study medication discontinuation and/or participant withdrawal (if applicable), must be recorded in the source documents. The eCRF must document the primary reason for discontinuation of study medication.

A specific monitoring plan must be agreed between the UCB study physician and the Investigator for study participants who have ALT >5 ULN. The monitoring plan should include any necessary follow-up assessments (until resolution of the abnormal lab values).

Phase 2 liver chemistry stopping criteria are designed to assure participant safety and to evaluate liver event etiology (Table 10-1).

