**Table 10-1: Phase 2 Liver Chemistry Stopping Criteria and Follow-up Assessments**

Liver Chemistry Stopping Criteria	
ALT-absolute	ALT $\geq$ 5xULN
ALT Increase	ALT $\geq$ 3xULN persists for $\geq$ 4 weeks
Bilirubina,b	ALT $\geq$ 3xULN and bilirubin $\geq$ 2xULN ( $>35\%$ direct bilirubin)
INRb	ALT $\geq$ 3xULN and international normalized ratio (INR) $>1.5$ , if INR measured
Cannot Monitor	ALT $\geq$ 3xULN and cannot be monitored weekly for 4 weeks
Symptomaticc	ALT $\geq$ 3xULN associated with symptoms (new or worsening) believed to be related to liver injury or hypersensitivity
Suggested Actions and Follow-up Assessments	
Actions	

Immediately discontinue study medication.

Report the event to the Sponsor within 24 hours.

Complete the liver event eCRF, and complete an SAE data collection tool if the event also met the criteria for an SAE.b

Perform liver chemistry follow-up assessments.

	
Follow-Up Assessments	

Viral hepatitis serologyd

Obtain INR and recheck with each liver chemistry assessment until the transaminases values show downward trend

Obtain blood sample for pharmacokinetic (PK) analysis as soon as possible after the most recent dosec

	

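### The protocol gives two different answers on whether study medication must stop when a liver chemistry stopping criterion is met: Section 7.1.2 leaves it to the Investigator, while Table 10-1 says stop at once

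*Protocol*

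**What the plan says.** - **Section 7.1.2** ties the stopping decision to the conditions in Figure 7-1 and words it as a matter for judgement: "Discontinuation of study medication for abnormal liver function should be considered by the Investigator". It adds that the Investigator may act on the participant's best interest.
- **Figure 7-1** is titled "Phase 2 liver chemistry stopping criteria and increased monitoring algorithm". Only the title can be read here; the body of the figure is not available.
- **Appendix 6 (Section 10.6)** has the word *suggested* in its title. Its opening says that participants with potential drug-induced liver injury "must be assessed to determine if study medication must be discontinued".
- **Table 10-1** lists six liver chemistry stopping criteria. Under "Suggested Actions and Follow-up Assessments", the first action is "Immediately discontinue study medication".
- **The Appendix 2 note** on safety laboratory tests refers to Section 7.1.2 and Appendix 6 and calls the actions found there *required*. The SAP note under Table 5-3 repeats that word.
- **Section 7.1.3 (QTc)** states without qualification that a participant who meets a criterion is withdrawn from study medication.

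**The concern.** A stopping criterion should give an Investigator and a monitor the same answer. Here, someone who reads Section 7.1.2 would conclude that continued dosing at ALT of at least 5xULN is allowed after due consideration. Someone who reads Table 10-1 would conclude that dosing has to end that day. Hepatotoxicity is one of the potential risks named in Section 2.3, based on clinical data, and the protocol mandates monthly liver tests in the first six months because of it. What is at stake is participant safety and even conduct between sites, together with a clear basis for judging whether continued dosing departed from the protocol. Nothing in the efficacy analysis depends on it.

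**Working it through.** No formula applies, so the check sets the texts side by side.

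**Step 1. What each text says about stopping**

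| Place | Force of the wording |
|---|---|
| Section 7.1.2 | Discretionary |
| Appendix 6 title | Suggested |
| Appendix 6 opening sentence | Case assessment to decide whether a stop is needed |
| Table 10-1 sub-heading over the actions | Suggested |
| Table 10-1 first action | Imperative, immediate stop |
| Table 10-1 rechallenge bullets | No restart without permission; permanent stop if it is refused |
| Table 10-1 footnote a | Imperative stop at ALT of at least 3xULN with bilirubin of at least 2xULN when fractionation is not to hand |
| Appendix 2 note | Required |

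**Step 2. Try each reading**

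- *Stopping is discretionary.* Then the first action in Table 10-1, its rechallenge bullets (which presuppose a stop), footnote a and the Appendix 2 note are all wrong.
- *Stopping is mandatory.* Then Section 7.1.2, the opening of Appendix 6, its title and the sub-heading in Table 10-1 are all wrong.

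Neither reading leaves the protocol consistent. The same actions are called suggested in one place and required in another.

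**Step 3. Scope**

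The criteria in Table 10-1 are: absolute ALT, persistent ALT, ALT with bilirubin, ALT with INR, ALT that cannot be monitored weekly, and ALT with symptoms. That makes 6.

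**Step 4. A neighbouring rule**

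Section 7.1.3 handles QTc with binding wording. The softer verb in Section 7.1.2 is therefore not simply the protocol's general style for stopping rules.

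**Step 5. Does other text settle it?**

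The appendix also says "A specific monitoring plan must be agreed between the UCB study physician and the Investigator" for participants with ALT above 5 ULN. That secures oversight, but it does not say whether dosing continues meanwhile.

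**The case against.** **Figure 7-1 cannot be read.** The verb in Section 7.1.2 attaches to the conditions in that figure, which covers monitoring as well as stopping. A soft verb may suit the monitoring branches, and the figure may itself instruct a stop. This stands as a limit: nothing here rests on what the figure lacks. It does not remove the problem, because the figure's title includes stopping criteria and the sentence introducing it would still say that stopping is only to be considered. The suggested-versus-required mismatch does not involve the figure at all.

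**The Section 7.2 list.** A reader might infer that liver stopping is optional because the list introduced by "Participants must be discontinued from study medication (but not necessarily from the study) if any of the following occurs" has eight items, including "Renal toxicity considered possibly related to the IMP", and none for liver. The documents do not support that inference. The QTc rule is plainly mandatory and is also missing from the list, so absence from it shows nothing about whether a rule binds.

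**Restart approval.** A reader might also see a conflict between Section 7.1.5 (agreement of the SMC) and Table 10-1 (Sponsor approval). Table 10-1 asks for Sponsor approval in addition to restart being allowed by the protocol, so the two approvals are cumulative.

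**Deviations.** It would go too far to say that continued dosing could never be classed as a deviation. Section 8 rules out waivers, SAP Section 5.1.2.2 has a category for withdrawal criteria, and the detailed criteria sit in a specification that is not among these documents.

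**Existing controls.** Section 7.1 requires a stop when the Investigator judges safety compromised. Section 8 requires immediate discussion of safety concerns with the Sponsor. Section 8.3.6 requires potential Hy's Law cases to be reported within 24 hours. Appendix 6 and Table 10-1 add the monitoring plan, 24-hour reporting and restart limits. These stand, and they keep the point small.

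**Conclusion.** The point holds as a contradiction in an operative dosing rule. Section 7.1.2 makes stopping discretionary, Table 10-1 makes it immediate for six criteria, and the protocol labels the same actions both suggested and required. It is a modest point. The number of participants affected cannot be derived from the documents, uneven stopping between sites is a possibility and not something the documents show, and no threshold, sample size or analysis is affected.

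The conclusion assumes that the stop branches of Figure 7-1 correspond to the criteria in Table 10-1. Their shared name makes this likely, but it is unconfirmed. It does not support a claim that participants are left unprotected.

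**What to change.** First check that the stop branches of Figure 7-1 match Table 10-1. Then:

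1. **Section 7.1.2.** State that a participant who meets a liver chemistry stopping criterion (stop branches of Figure 7-1; Table 10-1) will be discontinued from study medication immediately. Keep the Investigator's freedom to stop for other abnormal liver function in the participant's best interest. Say that the monitoring branches apply when no stopping criterion is met.
2. **Appendix 6.** Move the immediate stop and the 24-hour report to the Sponsor under a heading for required actions, and align the opening sentence with this. Keep the follow-up assessments as suggestions. Deleting *suggested* throughout could make tests such as liver imaging and/or biopsy binding, which is not intended.
3. **Section 7.2 (optional).** If a cross-reference is added, it should cover every binding stopping rule in Section 7.1, including QTc. Adding liver alone would create a new inconsistency.

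**Cost:** less Investigator discretion when a stopping criterion is met, and a protocol amendment with IRB/IEC approval. The change alters no threshold, visit, sample size or analysis. It helps only participants still on study medication when the amendment takes effect. If the sponsor in fact intends discretion, Table 10-1, its footnote a and the Appendix 2 note need correcting instead; an edit is needed either way.

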**Figure 7-1: Phase 2 liver chemistry stopping criteria and increased monitoring algorithm**

ALT=alanine aminotransferase; AST=aspartate aminotransferase; INR=international normalized ratio; SAE=serious adverse event; ULN=upper limit of normal.

Specific assessments and follow up actions for potential drug-induced liver injury are provided in Appendix 6 (Section 10.6).

